Subjects will be switched to open-label tofacitinib 5 mg BID for the remainder of the study.

- Contact IWRS and dispense new supply of open-label investigational product to subject;
- Administer in-clinic dose of investigational product from open-label study drug supply.
- Instruct subject not to take the in-clinic dose of investigational product the day of the next study visit but to bring the drug supply with them to the visit.

6.2.7. Week 24

There is a ± 7 day window for this visit.

- All PROs should be completed prior to any other study procedures. These include the following: ASAS/ASDAS_{CRP} Component: “Patient Global Assessment of Disease (NRS)”, “Patient Assessment of Spinal Pain” which includes Total Back Pain (NRS) and Nocturnal Spinal Pain (NRS), BASDAI (NRS), BASFI (NRS), and FACIT-F.

After the PROs are obtained, the following procedures should be completed prior to dosing:

- Verify morning dose of investigational product was not administered by subject. If the dose was administered, continue with visit but re-instruct subject on the requirement for in-clinic dosing;

- Note: For subjects where the visit is conducted in the afternoon or evening, verify the afternoon or evening dose of investigational product was not administered by the subject. Vital signs: Blood pressure (seated), pulse rate and temperature (via tympanic, oral or temporal, preferred);
- Laboratory testing: Hematology, Chemistry Panel, Urinalysis, Urine Pregnancy Test (for women of childbearing potential only), hsCRP;
- Administer in-clinic dose of investigational product from previously dispensed study drug supplies.

The following procedures can be done before or after dosing depending upon the clinic's schedule but it is recommended that they be done at the same time (before or after dosing) consistently across all subsequent subject clinic visits:

- Targeted physical examination (examination of heart, lungs, abdomen, lower extremities, skin (presence of rash) and lymph nodes);
- Weight (without shoes preferred);
- BASMI (linear function) by qualified blinded assessor: Lateral spinal flexion, tragus-to-wall distance, lumbar flexion (modified Schober), maximal intermalleolar distance and cervical rotation;
- Spinal mobility obtained by qualified blinded assessor: chest expansion;
- Assessment of swollen joints (44-joint count) by qualified blinded assessor;
- Assessment of enthesitis using the MASES Index by qualified blinded assessor;
- Complete drug accountability.

After dosing:

- Monitoring of adverse events and concomitant treatments. Record any modifications, deletions or additions;
- Contraception check: Confirm and document that proper contraception is being used;
- Contact IWRS and dispense new supply of investigational product to subject;
- Instruct subject not to take the in-clinic dose of investigational product the day of the next study visit but to bring the drug supply with them to the visit.

6.2.8. Week 32

There is a ± 7 day window for this visit.

Subjects are required to fast for at least 9 hours prior to the visit; however, blood collection for laboratory testing may be taken up to 48 hours prior to or following this visit as necessary to ensure the samples are collected in a fasting state. If the blood collection is completed in advance of the clinic visit, the PROs should not be done with the blood collection but at the clinic visit.

- All PROs should be completed prior to any other study procedures. These include the following: ASAS/ASDAS_{CRP} Component: “Patient Global Assessment of Disease (NRS)”, “Patient Assessment of Spinal Pain” which includes Total Back Pain (NRS) and Nocturnal Spinal Pain (NRS), BASDAI (NRS), BASFI (NRS), and FACIT-F.

After the PROs are obtained, the following procedures should be completed prior to dosing:

- Verify morning dose of investigational product was not administered by subject. If the dose was administered, continue with visit but re-instruct subject on the requirement for in-clinic dosing;

Note: For subjects where the visit is conducted in the afternoon or evening, verify the afternoon or evening dose of investigational product was not administered by the subject.

- Vital signs: Blood pressure (seated), pulse rate and temperature (via tympanic, oral or temporal, preferred);
- Laboratory testing: Central laboratory tests include: Hematology, Urinalysis, Chemistry Panel, Lipid Profile (fasting), Urine Pregnancy Test (for women of childbearing potential only), hsCRP;
- Blood sample for FACS Analysis;
- Administer investigational product to the subject from the previously dispensed study drug supplies.

The following procedures can be done before or after dosing depending upon the clinic’s schedule but is recommended that they be done at the same time (before or after dosing) consistently across all subsequent subject clinic visits:

- Targeted physical examination (examination of heart, lungs, abdomen, lower extremities, skin (presence of rash) and lymph nodes);
- Weight (without shoes preferred);

- Specific Medical History: History of uveitis, psoriasis, inflammatory bowel disease and peripheral articular involvement as assessed by swollen joint count;
- BASMI (linear function) obtained by qualified blinded assessor: Lateral spinal flexion, tragus-to-wall distance, lumbar flexion (modified Schober), maximal intermalleolar distance and cervical rotation;
- Spinal mobility obtained by qualified blinded assessor: chest expansion;
- Assessment of swollen joints (44-joint count) by qualified blinded assessor;
- Assessment of enthesitis using the MASES Index by qualified blinded assessor;
- Complete drug accountability.

Procedures to be performed after dosing:

- Monitoring of adverse events and concomitant treatments. Record any modifications, deletions or additions;
- Contraception check: Confirm and document that proper contraception is being used;
- Risk factor check for VTE ([Section 7.1.14](#));
- Contact IWRS and dispense new supply of study medication to subject;
- Instruct subject not to take the in-clinic dose of investigational product the day of the next study visit but to bring the drug supply with them to the visit.

6.2.9. Week 40

There is a ± 7 day window for this visit.

- All PROs should be completed prior to any other study procedures. These include the following: ASAS/ASDAS_{CRP} Component: “Patient Global Assessment of Disease (NRS)”, “Patient Assessment of Spinal Pain” which includes Total Back Pain (NRS) and Nocturnal Spinal Pain (NRS), BASDAI (NRS), BASFI (NRS), and FACIT-F.

After the PROs are obtained, the following procedures should be completed prior to dosing:

- Verify morning dose of investigational product was not administered by subject. If the dose was administered, continue with visit but re-instruct subject on the requirement for in-clinic dosing;

Note: For subjects where the visit is conducted in the afternoon or evening, verify the afternoon or evening dose of investigational product was not administered by the

subject. Vital signs: Blood pressure (seated), pulse rate and temperature (via tympanic, oral or temporal, preferred);

- Laboratory testing: Hematology, Chemistry Panel, Urinalysis, Urine Pregnancy Test (for women of childbearing potential only), hsCRP;
- Administer in-clinic dose of investigational product from previously dispensed study drug supplies.

The following procedures can be done before or after dosing depending upon the clinic's schedule but it is recommended that they be done at the same time (before or after dosing) consistently across all subsequent subject clinic visits:

- Targeted physical examination (examination of heart, lungs, abdomen, lower extremities, skin (presence of rash) and lymph nodes);
- Weight (without shoes preferred);
- BASMI (linear function) by qualified blinded assessor: Lateral spinal flexion, tragus-to-wall distance, lumbar flexion (modified Schober), maximal intermalleolar distance and cervical rotation;
- Spinal mobility obtained by qualified blinded assessor: chest expansion;
- Assessment of swollen joints (44-joint count) by qualified blinded assessor;
- Assessment of enthesitis using the MASES Index by qualified blinded assessor;
- Complete drug accountability.

After dosing:

- Monitoring of adverse events and concomitant treatments. Record any modifications, deletions or additions;
- Contraception check: Confirm and document that proper contraception is being used;
- Risk factor check for VTE ([Section 7.1.14](#));
- Contact IWRS and dispense new supply of study medication to subject;
- Instruct subject not to take the in-clinic dose of investigational product the day of the next study visit but to bring the drug supply with them to the visit.

6.2.10. Week 48

There is a ± 7 day window for this visit.

Subjects are required to fast for at least 9 hours prior to the visit; however, blood collection for laboratory testing may be taken up to 48 hours prior to or following this visit as necessary to ensure the samples are collected in a fasting state. If the blood collection is completed in advance of the clinic visit, the PROs should not be done with the blood collection but at the clinic visit.

- All PROs should be performed before any other study procedures at the clinic visit. These include the following: ASAS/ASDASCRP Component: “Patient Global Assessment of Disease (NRS)”, “Patient Assessment of Spinal Pain” which includes Total Back Pain (NRS) and Nocturnal Spinal Pain (NRS), BASDAI (NRS), BASFI (NRS), ASQoL, SF-36v2, EQ-5D-3L and EQ-VAS, FACIT-F, WPAI and AS-HCRU Questionnaire;
- Vital signs: Blood pressure (seated), pulse rate and temperature (via tympanic, oral or temporal, preferred);
- 12-lead electrocardiogram submitted to central reader;
- Laboratory testing: Central laboratory tests include: Hematology, Urinalysis, Chemistry Panel, Lipid Profile (fasting), Urine Pregnancy Test (for women of childbearing potential only), hsCRP;
- Blood sample for FACS Analysis;
- Complete Physical Examination: General appearance, skin (presence of rash), HEENT (head, eyes, ears, nose and throat), lungs (auscultation), heart (auscultation for presence of murmurs, gallops, rubs), lower extremities (presence of peripheral edema), abdominal (palpation and auscultation), neurologic (mental status, station, gait, reflexes, motor and sensory function, coordination) and lymph nodes;
- Weight (without shoes preferred);
- Specific Medical History: History of uveitis, psoriasis, inflammatory bowel disease and peripheral articular involvement as assessed by swollen joint count;
- BASMI (linear function) by qualified blinded assessor: Lateral spinal flexion, tragus-to-wall distance, lumbar flexion (modified Schober), maximal intermalleolar distance and cervical rotation;
- Spinal mobility obtained by qualified blinded assessor: chest expansion;
- Assessment of swollen joints (44-joint count) by qualified blinded assessor;

- Assessment of enthesitis using the MASES Index by qualified blinded assessor;
- Administer in-clinic dose of investigational product from previously dispensed study drug supplies;
- Complete drug accountability;
- Contraception check: Confirm and document that proper contraception is being used;
- Risk factor check for VTE ([Section 7.1.14](#));
- Monitoring of adverse events and concomitant treatments. Record any modifications, deletions or additions.

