5.3. Subject Compliance

Subject compliance with dosing administration will be verified by accounting of returned containers and investigational product at each visit. Compliance for the tablets will be calculated by each bottle and documented. If compliance is <80%, the investigator or designee is to counsel the subject and ensure steps are taken to improve compliance. Subjects, who are less than 80% compliant with the dosage regimen for any two consecutive visit periods, should be withdrawn from the investigational product. In the event that the investigational product is held due to an AE, infection or elective surgery, in accordance with the protocol-specified time frames, compliance should still be calculated for the visit period, but withdrawal from the investigational product would be assessed. If the subject is over-compliant with the investigational product (intentional or accidental) the investigator or designee is to counsel the subject and ensure correct understanding of the investigational product dosing regimen. The investigator should contact the Pfizer Medical Monitor or designee promptly with any over-compliance (>120%) that may potentially impact the safe use of the investigational product or that may result in a serious adverse event.

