5.5. Administration

Investigational product will be dispensed to subjects to self-administer after appropriate training and specific instructions are provided. Instructions on dosing will be provided on the Subject Dosing Card. At all visits, the scheduled dose of investigational product will be taken by the subject in the clinic. At the end of each visit, sites will instruct subjects, when to take their investigational product prior to their next study visit. [REDACTED]

[REDACTED] Subjects should receive open-label investigational product at the Week 16 visit and should receive the first dose of the open-label investigational product at the clinic.

Tofacitinib tablets or matching placebo for oral administration may be taken with or without food. Subjects will swallow the investigational product whole, and will not manipulate or chew the investigational product prior to swallowing.

Subjects will be instructed to take their tablet investigational product twice daily (once in the morning and once in the evening approximately 12 hours apart) for a total of two tablets per day. Placebo tablets will match the 5 mg tablets in order to maintain the blind.

During the double-blind treatment period, if the investigator deems it necessary to withhold the investigational product to treat a non-serious infection or other medical condition, temporary withholding is permitted for up to 5 days. If temporary withholding of the investigational product exceeding 5 days is required for a medical reason (eg, elective surgery), the investigator must contact the Pfizer Medical Monitor for approval.

Temporary withholding of the investigational product, as described above, is permitted once during the study without obtaining prior approval from the Pfizer Medical Monitor. Any additional request(s) for temporary withholding of the investigational product during the double blind period require(s) documented approval by the Pfizer Medical Monitor.

Per Amendment 3, for subjects with suspected VTE, treatment with tofacitinib should be temporarily withheld while the subject is evaluated. If VTE is confirmed, discontinue treatment with tofacitinib (see Section 6.4: Subjects Discontinuation from the Investigational Product).

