- BASMI (linear function) obtained by qualified blinded assessor: Lateral spinal flexion, tragus-to-wall distance, lumbar flexion (modified Schober), maximal intermalleolar distance and cervical rotation;
- Spinal mobility obtained by qualified blinded assessor: chest expansion;
- Vital signs: Blood pressure (seated), pulse rate and temperature (via tympanic, oral or temporal, preferred);
- Laboratory testing: Urine Pregnancy Test (for women of childbearing potential only), hsCRP;
- Assessment of swollen joints (44-joint count) by qualified blinded assessor;
- Administer investigational product from the previously dispensed study drug supplies unless subject had already administered dose at home;
- Complete drug accountability;
- Monitoring of adverse events and concomitant treatments. Record any modifications, deletions or additions;
- Contraception check: Confirm and document that proper contraception is being used;
- Instruct subject not to take the in-clinic dose of investigational product the day of the next study visit and to bring the drug supply with them to the visit.

6.2.3. Week 4

There is a ± 3 day window for this visit.

Subjects are required to fast for at least 9 hours prior to the visit; however, blood collection for laboratory testing may be taken up to 48 hours prior to or following this visit as necessary to ensure the samples are collected in a fasting state. If the blood collection is completed in advance of the clinic visit, the PROs should not be done with the blood collection but at the clinic visit.

- All PROs should be completed prior to any other study procedures. These include the following: ASAS/ASDAS_{CRP} Component: “Patient Global Assessment of Disease (NRS)”, “Patient Assessment of Spinal Pain” which includes Total Back Pain (NRS) and Nocturnal Spinal Pain (NRS), BASDAI (NRS), BASFI (NRS), and FACIT-F.

After the PROs are obtained, the following procedures should be completed prior to dosing:

- Verify morning dose of investigational product was not administered by the subject and previous day’s dosing was administered;

Note: For subjects where the visit is conducted in the afternoon or evening, verify the afternoon or evening dose of investigational product was not administered by the subject.

- Vital signs: Blood pressure (seated), pulse rate and temperature (via tympanic, oral or temporal, preferred);

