- Laboratory testing: Urine Pregnancy Test (for women of childbearing potential only), hsCRP;

- [REDACTED]

- [REDACTED]

The following procedures can be done before or after dosing depending upon the clinic's schedule but it is recommended that they be done at the same time (before or after dosing) consistently across all subsequent subject clinic visits:

- Targeted physical examination (examination of heart, lungs, abdomen, lower extremities, skin (presence of rash) and lymph nodes);
- Weight (without shoes preferred);
- Specific Medical History: History of uveitis, psoriasis, inflammatory bowel disease and peripheral articular involvement as assessed by swollen joint count;
- BASMI (linear function) by qualified blinded assessor: Lateral spinal flexion, tragus-to-wall distance, lumbar flexion (modified Schober), maximal intermalleolar distance and cervical rotation;
- Spinal mobility obtained by qualified blinded assessor: chest expansion;
- Assessment of swollen joints (44-joint count) by qualified blinded assessor;
- Assessment of enthesitis using the MASES Index by qualified blinded assessor;
- Complete drug accountability.

After dosing:

- 
- Monitoring of adverse events and concomitant medications. Record any modifications, deletions or additions;
- Contraception check: Confirm and document that proper contraception is being used;
- Contact IWRS and dispense new supply of investigational product to subject;
- Instruct subject not to take the in-clinic dose of investigational product the day of the next study visit and to bring the drug supply with them to the visit.

6.2.5. Week 12

There is a ± 7 day window for this visit.

- All PROs should be completed prior to any other study procedures. These include the following: ASAS/ASDASCRP Component: "Patient Global Assessment of Disease (NRS)", "Patient Assessment of Spinal Pain" which includes Total Back Pain (NRS) and Nocturnal Spinal Pain (NRS), BASDAI (NRS), BASFI (NRS), and FACIT-F.

After the PROs are obtained, the following procedures should be completed prior to dosing:

- Verify morning dose of investigational product was not administered by subject. If the dose was administered, continue with visit but re-instruct subject on the requirement for in-clinic dosing;

Note: For subjects where the visit is conducted in the afternoon or evening, verify the afternoon or evening dose of investigational product was not administered by the subject.

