- Vital signs: Blood pressure (seated), pulse rate and temperature (via tympanic, oral or temporal, preferred);
- Laboratory testing: Hematology, Chemistry Panel, Urinalysis, Urine Pregnancy Test (for women of childbearing potential only), hsCRP;
- Administer in-clinic dose of investigational product from previously dispensed study drug supplies.

The following procedures can be done before or after dosing depending upon the clinic's schedule but it is recommended that they be done at the same time (before or after dosing) consistently across all subsequent subject clinic visits:

- Targeted physical examination (examination of heart, lungs, abdomen, lower extremities, skin (presence of rash) and lymph nodes);
- Weight (without shoes preferred);
- BASMI (linear function) by qualified blinded assessor: Lateral spinal flexion, tragus-to-wall distance, lumbar flexion (modified Schober), maximal intermalleolar distance and cervical rotation;
- Spinal mobility obtained by qualified blinded assessor: chest expansion;
- Assessment of swollen joints (44-joint count) by qualified blinded assessor;
- Assessment of enthesitis using the MASES Index by qualified blinded assessor;
- Complete drug accountability.

After dosing:

- Monitoring of adverse events and concomitant treatments. Record any modifications, deletions or additions;
- Contraception check: Confirm and document that proper contraception is being used;

- Contact IWRS and dispense new supply of investigational product to subject;
- Instruct subject not to take the in-clinic dose of investigational product the day of the next study visit but to bring the drug supply with them to the visit.

6.2.6. Week 16

There is a ± 7 day window for this visit.

Subjects are required to fast for at least 9 hours prior to the visit; however, blood collection for laboratory testing may be taken up to 48 hours prior to or following this visit as necessary to ensure the samples are collected in a fasting state. If the blood collection is completed in advance of the clinic visit, the PROs should not be done with the blood collection but at the clinic visit.

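### At Weeks 12, 24, 32 and 40 the visit steps foresee a dose already taken at home but then list an in-clinic dose without the exception given at Week 2; Week 16 has a separate, related conflict

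*Protocol*

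**What the plan says.** Section 5.5 of the protocol (Administration) has subjects take one tablet "once in the morning and once in the evening approximately 12 hours apart) for a total of two tablets per day". The same section states, with no exception, "At all visits, the scheduled dose of investigational product will be taken by the subject in the clinic"; footnote 18 of the Schedule of Activities repeats this.

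The visit sections anticipate the subject who forgets and doses at home. At Weeks 2, 12, 16, 24, 32 and 40 the site checks whether the dose has been taken, and the text adds: "If the dose was administered, continue with visit but re-instruct subject on the requirement for in-clinic dosing".

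The administration steps then differ:

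- Week 2 (6.2.2): "Administer investigational product from the previously dispensed study drug supplies unless subject had already administered dose at home".
- Weeks 12, 24 and 40 (6.2.5, 6.2.7, 6.2.9): "Administer in-clinic dose of investigational product from previously dispensed study drug supplies".
- Week 32 (6.2.8): "Administer investigational product to the subject from the previously dispensed study drug supplies".
- Week 16 (6.2.6): "Administer in-clinic dose of investigational product from open-label study drug supply".

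For Week 16, Sections 5.4.1 and 5.5 and Schedule footnote 19 also say that the first open-label dose is taken in the clinic.

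**The concern.** One situation, a home dose before the visit, gets two different instructions depending on which visit section the site has open. At Week 2 the site is told not to give the dose again. At Weeks 12, 24, 32 and 40 the next dosing instruction carries no such condition, and a site following it gives a dose beyond the Section 5.5 schedule, possibly soon after the home dose.

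What is at stake is consistent delivery of the intervention and dosing safety. Sites that carry the Week 2 wording forward will act differently from sites that follow each section as written. Section 8.3.4.1 counts product taken at the wrong time as a medication error and wants the sponsor told immediately of a dosing error, so following the visit steps could produce an event that the protocol itself asks sites to report.

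**Working it through.** **Step 1: compare the visits.**

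| Visit (protocol section) | Checks that the dose was not taken | Says to continue if it was | Administration step |
|---|---|---|---|
| Week 2 (6.2.2) | yes | yes | exempts a dose taken at home |
| Weeks 4 and 8 (6.2.3, 6.2.4) | yes | no | partly redacted; not relied on |
| Week 12 (6.2.5) | yes | yes | no condition |
| Week 16 (6.2.6) | yes | yes | no condition; open-label supply |
| Week 24 (6.2.7) | yes | yes | no condition |
| Week 32 (6.2.8) | yes | yes | no condition |
| Week 40 (6.2.9) | yes | yes | no condition |
| Week 48 (6.2.10) | no | no | no condition, but no home-dose branch either |

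Weeks 12, 24, 32 and 40 share one pattern: the branch is present and the exception is absent.

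**Step 2: count tablets.** The plan's own figure (Section 5.5) is 1 morning + 1 evening = 2 per day.

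- Literal steps after a home dose: 1 at home + 1 in the clinic + 1 other scheduled dose = 3.
- Afternoon or evening visit, with that dose already taken: 1 morning + 1 at home + 1 in the clinic = 3.
- With the exception as worded at Week 2: 1 + 0 + 1 = 2, which agrees with Section 5.5. This shows only where the passages diverge; it is not a proposal for the rule.

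The site gives one of the three tablets. The total of three assumes that the subject also takes the other scheduled dose. No legible text tells the site or the subject to omit it.

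**Step 3: Week 16.** Giving the clinic dose after a home dose meets the first-open-label-dose requirement but departs from the two-tablet, 12-hour schedule. Withholding it keeps to that schedule but departs from Sections 5.4.1 and 5.5 and footnote 19. Neither course satisfies every passage. In the placebo sequence the home tablet is placebo, so three tablets would not mean three active tablets.

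**Step 4: would the compliance check show it?** Assume dosing is otherwise perfect.

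- 28-day interval (ending at Week 12): (2 × 28 + 1) / (2 × 28) = 57/56 = 101.8%.
- 56-day interval (ending at Week 24, 32 or 40): (2 × 56 + 1) / (2 × 56) = 113/112 = 100.9%.

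Both are far below the 120% over-compliance level in Section 5.3. One extra tablet barely moves counted compliance, and that threshold would not flag it.

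**The case against.** The strongest reply is that the in-clinic dose is by definition the scheduled dose. Section 5.5 says that the scheduled dose is taken in the clinic and sets two tablets a day; once that dose has been taken, nothing is left to administer. On this view the later visits lack a clause but do not order a second dose. The reading is reasonable and many sites will adopt it. It does not remove the problem: the sponsor thought the clause necessary at Week 2, and a general section does not clearly override an explicit step at the visit.

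Several other points stand and limit the claim:

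- Week 16 is not the same omission. Its unconditional wording matches the requirement for a first open-label dose in the clinic, and the SAP (Section 9.4, Table 5) takes the treatment switch date from the dosing log.
- Text is redacted in Section 5.5, directly after the sentence on instructing subjects when to dose before the next visit, and in the Week 4 and Week 8 steps. A rule may sit there unseen.
- Subjects are told at each preceding visit not to take the in-clinic dose at home on the next visit day. Over-compliance leads to counselling, and dosing errors are recorded. These controls make the event less likely or capture it, but they do not supply the missing rule.

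A reader might infer that the site itself hands out three tablets, that the Week 16 results are affected, or that compliance is materially inflated. The documents support none of these. The site gives one tablet. The four ASAS20 and ASAS40 domains are patient-reported and are collected before other procedures, and at Week 16 dosing is listed after the assessments. The compliance effect is 1 to 2 percentage points in one interval.

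**Conclusion.** The inconsistency is real and worth correcting, within the legible text. At four visits (Weeks 12, 24, 32 and 40) the administration step omits the exception that Week 2 gives for the same situation. Read literally, this adds one dose, making three tablets against two that day if the other scheduled dose is also taken. Week 16 is a fifth visit with a different conflict, between the first-open-label-dose requirement and the two-tablet rule.

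The size is per occurrence only. The documents do not say how often subjects dose at home before a visit, and any count would rest on an invented slip rate. The conclusion assumes that the redacted text holds no governing rule. No effect on an estimand, on the primary or key secondary analysis, or on counted compliance is claimed.

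**What to change.** The sponsor should reconcile the administration steps in Sections 6.2.5, 6.2.7, 6.2.8 and 6.2.9 with Sections 6.2.2 and 5.5. The text should state one explicit rule for a subject who has already taken that dose at home and use the same words at each visit. Section 6.2.6 should be reconciled separately with Sections 5.4.1 and 5.5 and Schedule footnote 19, so that the site knows what applies when a blinded dose was taken at home before the first open-label dose. Which dosing rule applies is for the sponsor to decide; this review takes no position on it.

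The cost is a wording change in a handful of visit sections, by amendment or a clarification letter to sites. It needs no new data, procedures or analyses.
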